2.6.1 Treatment for Overminus Group

NOTE: Details of spectacles to be prescribed will be automatically calculated by the study website.

No IXT treatment other than the study spectacles specified below can be prescribed at any time during the study unless the subject meets deterioration criteria described in section 3.7.

Enrollment Visit

- Subjects randomly assigned to the overminus group will be prescribed spectacles based on a cycloplegic refraction as follows:
 - o Fully correct the astigmatism in both eyes (if present)
 - Add -2.50D to the sphere component of the cycloplegic refraction for both eyes
- Overminus spectacles are prescribed to be worn all waking hours through the 12-month outcome visit.

12-Month Visit*

- At the 12-month outcome visit, overminus treatment will be discontinued and new nonoverminus spectacles will be prescribed based on the 12-month cycloplegic refraction as follows*:
 - If the cycloplegic refraction is spherical and plano or any amount of hyperopia in both eyes (with no astigmatism and no anisometropia), subjects will wear spectacles with plano lenses in both eyes to maintain masking.
 - Otherwise, fully correct astigmatism in both eyes and prescribe sphere as follows:
 - If least hyperopic eye has SE myopia:
 - Prescribe the full sphere in both eyes
 - If least hyperopic eye has SE hyperopia or emmetropia:
 - Prescribe sphere so that spectacles will have plano SE in the least hyperopic eye
 - Match any reduction of sphere made to the least hyperopic eye in the fellow eye
 - Subjects will wear the new prescription all waking hours until the 18-month visit.

* Unless the subject has already met deterioration criteria confirmed by masked examiner as described in section 3.7 in which case spectacles are prescribed at investigator discretion.

15-Month Visit*

- If the 12-month spectacles for a subject were issued **before** Protocol Amendment II and therefore contain partial-strength overminus (-1.25D), the spectacles should be changed to non-overminus spectacles at the 15-month to discontinue the overminus (see 12-month prescribing above).
- If the 12-month spectacles for a subject were issued **on/after** Protocol Amendment II and therefore are already non-overminus spectacles, the non-overminus spectacles should be continued at the 15-month visit.

* Unless the subject has already met deterioration criteria confirmed by masked examiner

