3.3 Masking of Treatment Group

Subjects will be masked to treatment group throughout the study. Subjects who do not have refractive error that requires correction (*see sections 2.6.1 and 2.6.2*) will be prescribed plano lenses if randomized to the non-overminus group.

1298 1299 1300

1301

1302

1303

1304

1305

Key outcome testing at each follow-up visit (*see section 3.3.1*) will be performed by an examiner masked to treatment group. Although the examiner will see the subject's spectacles during test, the presumption is that treatment group is unlikely to be discerned because 1) all subjects will be wearing spectacles and 2) because both treatment groups will have a range of prescriptions depending on subjects' underlying refractive error in addition to whether an overminus component is included. The Masked Examiner must be a pediatric ophthalmologist,

pediatric optometrist, or certified orthoptist. The Masked Examiner should preferably be someone *other than* the investigator.

If necessary at rare sites, the Masked Examiner may be the investigator if the investigator remains masked to the randomized treatment. At such sites, for prescription of spectacles throughout the study, the investigator should sign two prescriptions (one overminus prescription and one non-overminus prescription), after which an unmasked coordinator would provide the parent with the appropriate prescription according to the subject's treatment group.

 The investigator will be unmasked to treatment group except at rare sites in which he/she must serve as the masked examiner. The investigator should not discuss a subject's treatment group with the subject or his/her parents.

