3.3.1 Masked Examiner Testing

A masked examiner will assess the following at the 6-month, 12-month, 15-month, and 18-month visits regardless of whether or not the subject has already met deterioration criteria confirmed by masked examiner as described in *section 3.7* at a previous visit:

- Control assessment #1
- Stereoacuity
- Control assessment #2
- Cover test
- 1327 PACT
 - Control assessment #3
 - Assessment of deviation throughout the exam

The Masked Examiner must not verify the spectacles using lensometry, discuss compliance of spectacle wear with the subject or parents, or administer the symptom survey. The Masked Examiner should not review the subject's medical record prior to the exam.

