 - 10. Assessment of Deviation Throughout Exam (Masked)

1407 1408

The following procedures should be performed by either the Masked Examiner or another study-certified examiner:

14101411

1409

1412

1413

1414

1417

14181419

1420

1421

1422

1423

1424

- 11. Distance Visual Acuity Testing: Monocular distance visual acuity testing with the habitual correction and without cycloplegia will be measured using the same testing procedure as used for enrollment. Visual acuity may be tested at the start of the exam or before the cycloplegic refraction.
- 1415 12. Cycloplegic Autorefraction (12-month and 18-month visits only, mandatory if autorefractor is available at the site)
 - Refractive error must be measured with the same autorefractor used at enrollment following cycloplegia with 1% cyclopentolate (see cycloplegic refraction below).
 - If cycloplegic autorefraction was completed at enrollment, then it must be measured with the same autorefractor used at enrollment.
 - Regardless of whether cycloplegic autorefraction was completed at enrollment, it is mandatory to measure cycloplegic autorefraction if an autorefractor is available at the site.
 - Recorded values will be based on a single measurement by the instrument (which may be a mean of several individual measures depending on system)
- 1426 13. Cycloplegic Axial Length Measurement and Additional Biometry (18-month visit only) (see manual of procedures).

• Axial length

1433 1434

1435

1436

14371438

1439

14401441

1442

1443

1444

1445

1446

1447 1448

1449 1450

1451

14521453

1454

1455

1456

14571458

1459

1460

1461

1462

1463 1464

1465

1466

1467 1468 1469

1471

- Flat corneal radius
- Anterior Chamber depth
- Lens thickness, if available
- 1432 14. Cycloplegic Refraction (12-month and 18-month visits)
 - A cycloplegic refraction will be performed at the 12-month and 18-month visits. The cycloplegic refraction will be performed regardless of whether a cycloplegic autorefraction is performed.
 - Cycloplegic refraction is performed 30 to 45 minutes following at least one application of cyclopentolate 1% per investigator's usual dosage and timing routine.
 - The cycloplegic refraction is based on cycloplegic retinoscopy, which may be done with glasses off or as an over-refraction in front of the current spectacles. Subjective refraction is allowed.

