 - When an over-refraction of current eye glasses is performed, the reported cycloplegic refraction will be the sum of the current spectacle power and the over-refraction.
 - 15. ADHD and Seizure Medication Use Data Collection (12-month visit only)
 - At the 12-month visit, data regarding any ADHD and seizure medication use in the past 12 months will be collected.

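### Protocol 3.4 permits the Masked Examiner to do the 12-month cycloplegic refraction, even through the study spectacles, which can strongly indicate the arm before later masked grading

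*Protocol*

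**What the plan says.** Protocol 3.3 rests masking on the argument that every child wears spectacles and that prescriptions vary in both arms, so that "the presumption is that treatment group is unlikely to be discerned". Section 3.3.1 adds safeguards: "The Masked Examiner must not verify the spectacles using lensometry", and the examiner is also kept away from compliance discussion, the symptom survey and the medical record. Section 3.4 gives lensometry to someone else and has power markings on trial lenses covered. Section 3.3.1 then fixes the masked visits: "A masked examiner will assess the following at the 6-month, 12-month, 15-month, and 18-month visits".

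In Protocol 3.4, steps 11 to 15 follow the masked block (steps 4 to 10) under the sentence "The following procedures should be performed by either the Masked Examiner or another study-certified examiner". Step 14 is in that group: "A cycloplegic refraction will be performed at the 12-month and 18-month visits". It is based on retinoscopy, "which may be done with glasses off or as an over-refraction in front of the current spectacles". For an over-refraction, "the reported cycloplegic refraction will be the sum of the current spectacle power and the over-refraction".

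The overminus lenses come from Protocol 2.6.1: "Add -2.50D to the sphere component of the cycloplegic refraction for both eyes". They are worn until the 12-month visit. In the other arm (Protocol 2.6.2), children who are myopic in the least hyperopic eye get full correction. The rest get plano spherical equivalent in that eye.

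**The concern.** The safeguards in 3.3.1 and 3.4 exist to keep lens power from the person who grades the outcomes. Step 14 lets that same person put a retinoscope in front of the treatment lenses, and it defines the recorded result as a sum that includes lens power. The argument in 3.3 concerns what can be told from seeing spectacles. It does not cover refracting through them, where the underlying refractive error drops out and the lens offset is left.

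The distance control score is an examiner's judgement of how much of the time an eye drifts and how fast it recovers. If an examiner who has inferred the arm at 12 months grades the child again, observer bias can enter outcomes reported as masked. The main ones are 15- and 18-month distance control. They feed the secondary objective (Protocol 5.2, SAP 2.2) and the weaning and retention analyses (SAP 2.3). In the weaning analysis, an examiner who knows that treatment was reduced might expect worsening.

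**Working it through.** The plan states no figure for this, so there is none to reproduce. The check has four parts.

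**1. Timing.** Masked steps 4 to 10 are done without cycloplegia and come before step 14. The 12-month control scores are therefore already recorded when the refraction takes place. After 12 months (or after 15 months for children who were weaned) both arms should wear non-overminus lenses, so the 18-month refraction adds little. The refraction that matters is the one at 12 months.

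**2. Expected over-refraction.** Let R0 be the refraction at prescribing, R12 the refraction at 12 months and L the lens power.

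Over-refraction = R12 - L = (R0 - L) + (R12 - R0)

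Inputs:
- Offset R0 - L, overminus: +2.50 D (Protocol 2.6.1).
- Offset R0 - L, non-overminus: 0 D in myopes, up to +1.00 D at the hyperopic entry limit (Protocol 2.2 and 2.6.2).
- Mean 12-month change: -0.42 D and -0.05 D (Protocol Amendment II, rationale for change 1).

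Results:
- Overminus: 2.50 - 0.42 = +2.08 D.
- Non-overminus: 0 - 0.05 = -0.05 D, up to 1.00 - 0.05 = +0.95 D.
- Gap between arms: 2.08 - 0.95 = 1.13 D, up to 2.08 + 0.05 = 2.13 D.

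**3. Individual children.** Amendment II reports changes of more than 1.00 D in 29 of 168 overminus children and 3 of 146 non-overminus children. Assume these changes were all myopic. Then (168 - 29)/168 = 139/168 = 83% of overminus children would show at least 2.50 - 1.00 = +1.50 D, ignoring the 0.50 D lens tolerance in Protocol 3.4. A non-overminus child at the +1.00 D limit would need a hyperopic shift of at least 0.50 D to reach that value.

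**4. How well one reading separates the arms.** Assuming normal changes, the SD follows from the mean and the share beyond 1.00 D:
- Overminus: 29/168 = 0.173, so SD = (1.00 - 0.42)/0.944 = 0.61 D.
- Non-overminus: 3/146 = 0.021, so SD = (1.00 - 0.05)/2.043 = 0.47 D.

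A simulation of one million children per arm gave the area under the ROC curve (AUC) and the accuracy at the best cutoff with the arms equally weighted. The noise SD covers measurement and lens error and is assumed. So is the mix of non-overminus offsets, which the documents do not give.

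| Non-overminus offset | No noise | Noise SD 0.25 D | Noise SD 0.50 D |
|---|---|---|---|
| all 0 D | AUC 0.997, 98% | 0.994, 96% | 0.979, 93% |
| uniform 0 to +1.00 D | 0.976, 92% | 0.965, 90% | 0.934, 86% |
| all +1.00 D | 0.929, 85% | 0.909, 83% | 0.860, 78% |

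The arm would be guessed correctly in about 78 to 98% of children from the over-refraction alone. Knowing the lens power as well would make the offset explicit. A glasses-off refraction with lens power unknown does not show the arm.

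**The case against.** The strongest reply is that the risk needs a chain of options. The Masked Examiner must be the one who refracts, over-refraction must be chosen over glasses-off, and the same person must examine that child again. Protocol 3.4 permits the first two and requires neither. Protocol 3.3.1 asks for a masked examiner at each visit, not the same one. The investigator is normally unmasked and so is usually available to refract. All of this stands, and it limits how often the problem can arise.

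It can also be said that Protocol 3.3 and 3.5 already require a masked examiner, so anyone who has learned the arm is disqualified. That is the intent. But no passage tells a site that having refracted the child disqualifies the examiner, and a general requirement does not cure an explicit permission that undermines it.

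Other points stand in part. Protocol 3.4 does not say that the refractor does the addition, so lens power could be added by someone else; the over-refraction would still carry the signal. The control scale has timed criteria, and the examiner would have to remember the finding for three to six months. Stereoacuity depends on the child's responses at fixed test levels, so it is less open to bias than control. The procedures manuals are not available here and may name the refractor.

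A reader might infer that the protocol itself unmasks the examiner, that the arm is revealed in every child, or that the trial's main result is compromised. The documents support none of these. The route is optional, the inference is probabilistic, and the primary outcome is recorded first. Adding the 24- and 36-month visits would not enlarge the concern much, since SAP 5.4 treats control, alignment and stereoacuity there as exploratory and without p-values.

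**Conclusion.** The gap is real but conditional. Section 3.4 permits a procedure that conflicts with the protocol's own masking safeguards, and where it is used it strongly indicates the arm in most children: +2.08 D against -0.05 to +0.95 D on average, with about 78 to 98% classified correctly. That range rests on normal changes, on counting all changes over 1.00 D as myopic, and on the assumed noise and offset mix.

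The 12-month primary comparison is not touched. Exposed, if the same person returns to the child, are mainly 15- and 18-month distance control and, less so, the stereoacuity retest after 12 months. The number of children affected cannot be derived from the documents, so no size of bias can be given. The point merits a change of wording and a disclosure; it does not show that the 18-month result is biased.

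**What to change.** In Protocol 3.4, remove the Masked Examiner from those who may do the 12-month cycloplegic refraction. Where the investigator has to be the Masked Examiner, require a glasses-off refraction, with other staff taking the spectacles away first and lens power withheld. Glasses-off is already an allowed method. Record who refracted from now on.

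The wording change has short reach in this trial. Amendment II counts 37 twelve-month visits outstanding on 5 November 2019 against 355 expected 18-month visits (37/355 = 10%). For visits already completed, repeat the 18-month distance control comparison excluding examinations by someone who had refracted that child, but only where site records identify the refractor. Elsewhere, report possible unmasking as a limitation. A new case report form field cannot recover this for earlier visits.

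The cost is one sentence, one field, minor scheduling at small sites and one sensitivity run. That run will be incomplete and will partly select children by how their site was staffed, so it should be read as supportive only. No sample size figure changes.

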3.5 Repeat Stereoacuity Testing on a Subsequent Day

At any follow-up visit (including the 18-month outcome visit), subjects whose near stereoacuity by the Randot Preschool Stereoacuity test is worse by 2 octaves or more from baseline on both the initial test and the same-day retest by a Masked Examiner must return for a retest of stereoacuity by a masked examiner on a subsequent day. This return visit must be within 1 month of the follow-up visit (including the 18-month outcome visit).

- This return visit must also be after the child has received his/her new glasses prescribed at the follow-up visit (applies only to the 12-month and 15-month visits).
- A Masked Examiner must test the stereoacuity at this repeat visit. If stereoacuity is still reduced 2 octaves or more from baseline, stereoacuity is retested after a short rest period.
 - o If the stereoacuity has worsened by 2 octaves or more from baseline (confirmed by a retest), the investigator may initiate non-randomized treatment for IXT at his/her discretion (see section 3.8)
 - o If stereoacuity has not worsened by 2 octaves or more from baseline, the subject will continue the randomized treatment unless the subject has already met deterioration criteria at a previous visit confirmed by masked examiner as described in *section 3.7* in which case spectacles are prescribed at investigator discretion.
- No testing other than stereoacuity testing is required.

3.6 Additional Visits

1470 Investigators may schedule additional visits at their own discretion.

If the investigator plans to initiate non-randomized treatment for IXT at an additional visit, a masked examination (following all testing procedures in *section 3.4* except for the cycloplegic

refraction / autorefraction) must be performed prior to initiating the new treatment. If a masked examiner is unavailable, data from an unmasked exam should be entered on the website, noting that the examiner was unmasked. If the investigator is starting non-randomized treatment, the subject does not return for a stereoacuity retest if stereoacuity is decreased (section 3.7).

3.7 Deterioration Criteria

Subjects who meet either of the following at any visit will be considered to have met deterioration criteria.

- Motor deterioration: Control of the exodeviation measures 5 (constant exotropia) on all three assessments at distance and near. The exodeviation does not need to be constant throughout the entire exam provided that it is constant during all three control testings.
- Stereoacuity deterioration: Drop in near stereoacuity of at least 2 octaves (as defined in section 3.4) (at least 0.6 log arcsec) from enrollment stereoacuity, or to nil, confirmed by a retest by a Masked Examiner on a subsequent day (section 3.5). Note: subjects with nil stereoacuity at enrollment will not be able to deteriorate with respect to a drop in near stereoacuity.

Subjects who meet deterioration criteria may have non-randomized treatment for IXT started at investigator discretion. Whether or not a subject starts non-randomized treatment for IXT during the study, all subjects will still be followed at regular study visit intervals through the end of the study.

3.8 Initiating Non-Randomized Treatment for IXT

Non-randomized treatment for IXT is not permitted during the study unless the subject has met deterioration criteria (*see section 3.7*). If neither deterioration criterion is met but the subject is experiencing overwhelming social concerns or significant symptoms associated specifically with the exodeviation, the investigator must call the protocol chair to discuss the case and obtain approval for an exception prior to initiating non-randomized treatment for IXT.

Non-randomized treatment for IXT refers to any treatment other than that which the subject was randomized to. It includes but is not limited to:

- 1506 Surgery
 - Occlusion
 - Vergence exercises
 - Overminus spectacles (in non-overminus group)
 - Cycloplegia

• Formal discontinuation of overminus spectacles (in overminus group) – note that subject non-compliance with overminus spectacles is not considered formal discontinuation.

If the investigator plans to initiate non-randomized treatment for IXT at an additional visit rather than a protocol-specified visit, a masked examination must be performed prior to initiating the new treatment (section 3.6).

Subjects who have started non-randomized treatment for IXT during the study will still be followed at regular study visit intervals through the end of the study.

1522 3.9 **Treatment of Amblyopia**

Given the exclusion of subjects with amblyopia, the rate of developing amblyopia during the study is expected to be low. Nevertheless, if amblyopia develops during the study, the investigator may initiate amblyopia treatment, however initiating atropine, other cycloplegic drops, or levodopa is not allowed.

1526 1527

1523

1524

1525

Management of Refractive Error

1528 Management of refractive error will follow study guidelines (see sections 2.6.1 and 2.6.2) for 1529 1530 the duration of the study. A cycloplegic refraction will be performed for all subjects at the 12-1531 month visit and the 18-month visit. These data are used to adjust the glasses at 12-,15- and 18-1532 month visits.

CHAPTER 4: MISCELLANEOUS CONSIDERATIONS

4.1 Contacts by the Jaeb Center for Health Research

The Jaeb Center serves as the PEDIG Coordinating Center. The Jaeb Center will be provided with the parent's contact information. The Jaeb Center will contact the parents of the subjects only when necessary. Permission for such contacts will be included in the Informed Consent Form. The principal purpose of the contacts will be to develop and maintain rapport with the subject and/or family and to help coordinate scheduling of the outcome examinations.

4.2 Subject Withdrawals

Parents may withdraw their child from the study at any time. This is expected to be a very infrequent occurrence in view of the study design's similarity to routine clinical practice. If the parents indicate that they want to withdraw their child from the study, the investigator personally should attempt to speak with them to determine the reason. If their interest is in transferring the child's care to another eye care provider, every effort should be made to comply with this and at the same time try to keep the subject in the study under the new provider's care.

4.3 Risks

There are no risks involved in this study that would not be part of usual care when treating with either overminus or non-overminus lenses.

4.3.1 Risks of Examination Procedures

The procedures in this study are part of daily eye care practice in the United States and Canada and pose no known risks.

4.3.2 Risk of Overminus Lens Therapy

The risks involved in the study are identical to those for a child treated with overminus lens therapy who is not participating in the study.

Some subjects treated with overminus lenses may experience eye strain when wearing the spectacles; the eye strain typically dissipates with removal of the spectacles.

Among previous retrospective reports, some have indicated that there may be an increased rate of myopia development when accommodation is stimulated, 11,18,31 whereas others have reported no increase in myopia following overminus lens therapy. However, unpublished data from the current ongoing randomized trial suggests that myopic progression over one year is greater in subjects treated with overminus lenses vs. those treated with non-overminus lenses, and that myopic progression was most often observed in overminus group subjects who had spherical equivalent myopia of -0.50 D or greater at baseline (PEDIG unpublished, 2019).

